6.5.4.1 Adverse Events

Definition of Adverse Events

An adverse event is any untoward medical occurrence in a patient or clinical investigational patient administered a medicinal product and which does not necessarily have to have a causal relationship with this treatment. An adverse event can therefore be any unfavorable and unintended sign (including an abnormal laboratory finding, for example), symptom, or disease temporally associated with the use of a medicinal product, whether or not considered related to the medicinal product.

In this study, adverse events will be captured from the time a patient signs the ICF to the Follow-up Visit and include the following:

- Any new sign, symptom, or disease;
- Any new clinically significant or symptomatic laboratory/diagnostic test abnormality;
- Any clinically significant worsening of laboratory/diagnostic test abnormality;

- Any worsening (ie, clinically significant change in frequency, nature, and/or intensity) of a pre-existing condition.

A pre-existing condition is a condition that is present prior to signing the ICF for the study. Pre-existing conditions, such as illnesses, symptoms, reactions, progression of disease states, and other comorbidities, as well as laboratory/diagnostic test abnormalities, will be documented in the patient's record as medical history.

Signs and symptoms will be reported individually as adverse events (non-serious), unless a medical diagnosis was provided. Medical diagnosis, whenever provided, will be reported rather than individual signs and symptoms.

Any adverse event that satisfies any of the seriousness criteria described below will be reported as an SAE using the SAE Report Form, in addition to documenting in the eCRF. Serious adverse events that occurred up to 30 days after the last dose of study drug need to be documented on an SAE Report Form if they are deemed by the Investigator to be "Related" to study drug.

Adverse Event Severity Assessment

The Investigator will assess the severity (ie, intensity) of each adverse event (serious and non-serious) reported during the study based on his/her clinical judgment. The severity of each adverse event will be assigned to one of the following categories:

- Mild:** Transient, requires no special treatment, is easily tolerated by the patient, causes minimal discomfort, and does not interfere with the patient's daily activities

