Every effort should be made by the Investigator to explain each adverse event and assess its relationship, if any, to study drug. The Investigator should consider many factors, including, but not limited to, temporal association of the event and date/time of study drug, duration of study drug, medical/biologic plausibility, pharmacology and adverse event profile of study drug, medical history (past medical history, underlying disease, comorbidities, intercurrent illness), concomitant medications, medical judgment, dechallenge, rechallenge, drug interaction, other plausible causes, etc., to determine the causality assessment of an event.

The Investigator as well as the Sponsor will determine adverse event/SAE causality as ‘Related’ or ‘Not Related’ to study drug. Although there is no international consensus on how to define ‘Related’ and ‘Not Related,’ in general, an event is considered ‘Related’ if there is reasonable possibility that the event is related to study drug than to any other possible cause(s). Conversely, an event is considered ‘Not Related’ if there is reasonable possibility that the event is related to other factors than the study drug.

Adverse Event Documentation and Follow-up

All adverse events, including observed, elicited, or volunteered problems, complaints, or symptoms are to be recorded on the adverse event page in the patient’s eCRF from the time the patient signs the ICF and until the Follow-up Visit/early termination, whether or not judged by the Investigator to be related to study drug. The need to capture this information is not dependent upon whether adverse events are related to study drug. Serious adverse events that occurred up to 30 days after the last dose of study drug need

to be documented on an SAE Report Form if they are deemed by the Investigator to be “Related” to study drug.

Each adverse event is to be documented with a verbatim/reported term, start and stop date and time, severity, causal relationship to study drug, action taken with study drug, and outcome (resolved, resolved with sequelae, resolving, fatal, unknown). The Investigator must review new adverse events and the outcome of ongoing adverse events frequently throughout the study.

In addition to recording all adverse events (serious and non-serious) in the patient’s eCRF, all SAEs must also be documented on the SAE Report Form for the study.

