6.5.4.5 Electrocardiogram

The 12-lead ECGs will be obtained prior to the start of dialysis and will be read locally by the Investigator or qualified designee. Electrocardiograms read by a qualified designee must be endorsed by the Investigator. Clinically significant abnormalities or worsening findings observed after the first dose of study drug will be reported as treatment-emergent adverse events (TEAEs).

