9.2 Adverse Events

The period of adverse event reporting will start after the signing of the informed consent form (ICF) through the study Follow-up Visit or Early Termination Visit (or 7 days after the last dose if no Early Termination Visit was conducted). All adverse events that occur during this reporting period will be collected for all subjects, including subjects who are deemed to be screen failures.

Treatment-emergent adverse events (TEAEs) relative to the Double-blind Treatment Period are identified as any adverse event with an onset date after the first dose of the study drug up to the study End of Treatment/Early Termination Visit or the start of the Discontinuation Period or 7 days after the last dose if no End of Treatment/Early Termination Visit was conducted, whichever is later.

Adverse events that are considered “treatment-emergent” relative to the Discontinuation Period are identified as any adverse event with an onset date after the start of the Discontinuation Period through up to 2 weeks after this time point or the start of the Open-label Treatment Period, whichever comes first.

All tabular adverse event summaries will be for TEAEs by period.

For events with missing start dates, the following criteria will be used:

- If the start date for a particular event is missing, then the event is considered treatment-emergent for the Double-blind Treatment Period, unless the end date is reported and prior to the Double-blind Treatment Period start date.
- If a partial date is consistent with being in more than 1 period, then the ordering of assignment preference will be: Double-blind Treatment Period, Discontinuation Period, and Run-in Period. So if a partial date was consistent with the Double-blind Treatment Period and Discontinuation Period, it would be assigned to the Double-blind Treatment Period.
- If the start time is missing and the start date is the same as the start of a given period, the adverse event will be considered to have occurred in that period.

All adverse events will be coded to SOC and preferred term using the MedDRA version 20.1. The MedDRA treatment dictionary will be used to map adverse events verbatim to SOC and preferred term for standardization and summary purposes.

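### Treatment-emergence is decided by onset date alone, so an adverse event that begins between consent and first dose and then worsens on study drug drops out of the Double-blind adverse event tables unless the site opens a new record

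*SAP*

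**What the plan says.** SAP 9.2 defines a treatment-emergent adverse event (TEAE) for the Double-blind Treatment Period as "any adverse event with an onset date after the first dose of the study drug", up to the end-of-treatment or early termination visit, with alternative end points for the window. For the Discontinuation Period it is "any adverse event with an onset date after the start of the Discontinuation Period through up to 2 weeks after this time point", or until open-label treatment starts if that is sooner. Both definitions use onset date only. Protocol 8.8.2 uses the same onset criterion, so it does not supply what the SAP leaves out. SAP 9.2 then says "All tabular adverse event summaries will be for TEAEs by period".

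Adverse events are collected from consent. The Screening Visit falls 7 to 28 days before randomization, or within the 7-day Run-in at the investigator's discretion (SAP 2.2.1).

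Protocol 6.5.4.1 makes worsening of a pre-existing condition an adverse event in its own right, but limits the term: "A pre-existing condition is a condition that is present prior to signing the ICF for the study". On record structure it says "Each adverse event is to be documented with a verbatim/reported term, start and stop date and time, severity", among other items. Neither document says whether a change in severity or seriousness opens a new record.

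**The concern.** Some adverse events will have an onset after consent and before the first dose. The Run-in Structured Safety Evaluation asks about mental status change, falls and gait disturbance, which are also special-interest categories in SAP 9.2. If such an event is mild in Run-in and becomes severe or serious on study drug, the stated rule leaves it outside the tables that compare the arms.

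No safety testing is planned (Protocol 8.8), so the descriptive adverse event tables are the main between-arm safety display. A listing shows the event but gives no comparison by arm. The omission also runs against the SAP's otherwise cautious conventions. A missing start date normally counts as treatment-emergent in the Double-blind Treatment Period, missing severity counts as severe, and missing relationship counts as related. A documented worsening on drug gets no such treatment.

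**Working it through.** No arithmetic applies, because the point concerns a definition. The check traces each kind of worsening event through the collection rules, the TEAE definitions and the planned displays.

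- **Condition present before consent that worsens after first dose.** Protocol 6.5.4.1 makes the worsening a new adverse event. It can carry a post-dose onset date and is counted as a TEAE.
- **Laboratory or diagnostic abnormality that worsens.** Protocol 6.5.4.1 lists a clinically significant worsening as an adverse event, with no requirement that the abnormality predate consent. It is counted.
- **Examination or ECG finding that worsens after first dose.** Protocol 6.5.4.3 and 6.5.4.5 have it reported as a TEAE. It is counted.
- **Event with onset between consent and first dose that worsens or becomes serious on drug.** It is not pre-existing in the protocol's sense, so the worsening rule does not reach it. With its original onset date it fails the test in SAP 9.2. It is then absent from the Double-blind TEAE, serious, severe, special-interest and incidence-rate tables. Protocol 8.8.2 defines events emergent relative to Run-in, but SAP 9.2 itemizes tables only for the Double-blind Treatment and Discontinuation Periods, so the event may be in no adverse event table at all.
- **Event with onset on double-blind drug that intensifies after Day 85.** It is a Double-blind TEAE and is tabulated there. It fails the Discontinuation Period test, "any adverse event with an onset date after the start of the Discontinuation Period", so the adverse event tables for that period do not show it.

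Other displays pick up part of the fourth case. The all-event, serious-event and death listings in SAP 9.2 are not limited to TEAEs. SAP 10.4 tabulates in-patient hospitalization by treatment for each study period, whatever the onset date. If the patient stops study drug, the reason is counted in the disposition table (SAP 5.1), without the event term.

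One partial safeguard has gone. For each period, the overall table in Protocol 8.8.2 counts patients with any adverse event, emergent or not. The overall summary in SAP 9.2 has no such row, SAP Section 12 does not list the removal, and SAP Section 1 gives the SAP precedence over the protocol.

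**The case against.** The strongest objection is that the gap depends on documents not in hand. The protocol lists severity among the items recorded for each event, but does not say that an event has one fixed severity or that worsening cannot open a new record. SAP 9.2 itself allows for the same TEAE occurring more than once in a patient with different severity ratings. If the eCRF instructions require a new record on worsening, the onset rule works and the gap closes. This stands as a condition on the conclusion. It does not remove the need to state the rule, because the TEAE definition relies on it.

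A reader might also infer more than the documents support:

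- *That these events appear in no safety table.* They do not appear in the adverse event tables, but hospitalization is tabulated by period regardless of onset, and three other kinds of worsening are already captured.
- *That physical dependence would go undetected.* An event carried past Day 85 is already in the Double-blind tables. ShOWS scores feeling sick, aches and insomnia daily, and SAP 10.5 compares ShOWS and OOWS between arms by ANCOVA with the Day 85 value as covariate. That covers intensification after stopping without using adverse event onset, although only for symptoms on those scales.
- *That the onset rule contradicts the ECG and examination provisions.* A worsening finding can be reported with a post-dose onset date and so meet the rule. Those provisions show that the protocol means on-drug worsening to count; they do not conflict with SAP 9.2.
- *That the loss can be sized against the 2% threshold for common TEAEs.* That threshold applies to single preferred terms, whereas the gap runs across all terms, and the documents give no rate of ongoing or worsening events.

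**Conclusion.** The concern holds for a defined group: adverse events that start between consent and first dose and then increase in severity or become serious on study drug. Under the rule as written they are left out of the Double-blind adverse event tables, including the serious, severe, special-interest and incidence-rate tables. The omission is in the direction of under-counting on-drug harm. The Discontinuation Period gap is real but secondary, since the event is tabulated in the earlier period and the withdrawal scales partly cover its intensification.

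The conclusion assumes that sites do not already open a new record when an event worsens. The documents are silent on this. The number of patients affected cannot be estimated from them.

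**What to change.** In SAP 9.2, define a TEAE for each period as an adverse event that starts in that period, or that was present before it and increases in severity or becomes serious during it. State, in the SAP and the eCRF instructions, that a worsening is entered as a new record with its own onset date. For data already collected, use any dated change in severity or seriousness on the adverse event or SAE forms. Either restore the protocol's per-period count of all adverse events, emergent or not, or declare its removal in SAP Section 12.

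The cost is a few sentences, a few more adverse event records and slightly higher TEAE counts in both arms. The remedy may be incomplete for existing data. The SAP cites regulatory advice of 10 January 2019 against a protocol dated 21 December 2017, so a new recording rule may come too late for some records, and those without dated severity changes cannot be fully reclassified.

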2.6 Sample Size Determination

The planned sample size for this study is 350 (175 per treatment group) male and female hemodialysis subjects with chronic moderate-to-severe pruritus (mean baseline 24-hour Worst Itching Intensity NRS score >4), randomized at approximately 80 clinical sites. The sample size may be increased to 500 subjects (250 per treatment group) based on the results of a planned unblinded interim assessment conducted when approximately 50% of the planned 350 first subjects have been randomized and have either completed the 12-week Double-blind Treatment Period or have discontinued from treatment early. The planned interim assessment will be conducted by an Independent Data Monitoring Committee (IDMC). Details related to the sample size re-estimation are included in Section [11](#).

The sample size calculation is based on results of a completed phase 2 double-blind, placebo-controlled study (CR845-CLIN2101) of CR845 in hemodialysis subjects with ESRD who had moderate-to-severe pruritus. In this study, 30% of subjects randomized to the placebo group reported ≥ 3 -point improvement from baseline with respect to the 24-hour Worst Itching Intensity NRS at the end of treatment (Week 8). The proportion of subjects who received CR845 and reported a similar improvement in itch scores ranged from approximately 60% to 45% (i.e., 30% to 15% difference from placebo), depending on the dose of active study drug (0.5 mcg/kg, 1.0 mcg/kg, 1.5 mcg/kg).

Given a sample size of 350 subjects (175 per treatment group) and assuming a true response rate of 30% for the placebo group and a true response rate of 50% for the CR845 group (defining response as an improvement from baseline ≥ 3 points with respect to the Worst Itching Intensity NRS at Week 12), a 2-sided continuity corrected Chi-square will have 96% power to detect a treatment difference. The power of this test statistic would be $\geq 84\%$ for differences from placebo as low as 0.16 ([Table 1](#)).

Table 1 Power as a Function of Odds Ratio (N = 175 per arm)

Placebo Response	0.30	0.30	0.30	0.30
CR845 Response	0.50	0.48	0.46	0.45
Odds Ratio	2.333	2.154	1.988	1.909
Power^a	96%	92%	84%	79%

a. Power for a 2-sided Chi-square continuity-corrected test and a 5% Type 1 error.

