6.2 Baseline Disease Characteristics

Baseline characteristics of the disease will also be summarized by treatment group and include the following:

- Duration of pruritus (years)
- Years since ESRD
- Years since chronic kidney disease (CKD)
- Years on chronic hemodialysis
- Etiology of CKD
- Baseline Worst Itching Intensity NRS
- Anti-itch medication use during the Run-in Period (stratification factor)
- Presence of specific medical conditions (stratification factor)

Duration of pruritus (years) will be calculated as:

(Date of the Screening Visit – the start date of the pruritus+ 1)/365.25.

Years since ESRD will be calculated as:

(Date of the Screening Visit – first date of ESRD+ 1)/365.25.

Years since CKD will be calculated as:

(Date of the Screening Visit – first date of CKD+ 1)/365.25.

Years on chronic hemodialysis will be calculated as:

(Date of the Screening Visit – date of first chronic hemodialysis + 1)/365.25.

For each of the above, if partial dates are recorded, the first day of the month will be imputed for missing day, and January for missing month.

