7. STUDY DRUG EXPOSURE AND TREATMENT COMPLIANCE

For this study, the duration of double-blind treatment for each individual subject is expected to be 12 weeks, for a total of approximately 36 doses of study drug administered immediately following each dialysis session.

The following variables will be summarized by treatment group to describe the duration of exposure and length of participation in the Double-blind Treatment Period:

- Duration of double-blind treatment (days) as: (Date of first dialysis after last dose) – (Date of first double-blind dose) + 1.
- Duration of double-blind phase (days), from first double-blind dose to final assessment in the discontinuation period. This will be (End of double-blind participation date, including Discontinuation Period) – (Date of first double-blind dose) + 1.
- Average dose per administration (mcg/kg)

The following measures will be used to assess compliance:

- Total number of double-blind doses actually received (1-3, 4-6, 7-9, etc.)
- Total number of dialysis visits logged (1-3, 4-6, 7-9, etc.)
- Number of missed doses
- Number of missed dialysis visits
- Number of subjects with extra doses
- Number of subjects with extra dialysis visits

If a subject receives additional dialysis during a given week for any reason, an additional dose of CR845 will be administered following dialysis. A maximum of 4 doses per week is allowed. No additional doses will be given for subjects receiving an additional unscheduled ultrafiltration treatment. The number of subjects getting such an extra treatment will be summarized.

Missed and extra doses/dialysis will be determined as follows:

1. Individual weeks for each subject are examined.
2. Each subject should have 3 doses per week up to the final week of the period. Anything more will be counted as extra doses; anything less will be counted as missed doses.
3. Subjects who do not complete through the final week of the period will be checked for how far they were into the week that they discontinued: 1,2 days means that they should have 1 dose; 3,4 = 2 doses; 5 or more = 3 doses. This will be compared to actual doses for that week to determine missed/extra.
4. The missed and extra doses are then summed across each subject's weeks to get the total missed and extra.

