Incidence rate will be calculated for AESIs, serious TEAEs, and TEAEs leading to death, and will be summarized by SOC and preferred term. Incidence rate will be calculated as $(1000 * \text{the number of events}) / \text{total person-years}$, where total person-years is the sum across all subjects in the treatment group of the individual subject risk times, and individual subject risk time is the number of days from first dose to the last day of the period where an event would be deemed to be treatment emergent.

The following summary tables will be presented for the Double-blind Treatment Period:

- An overall summary showing for each treatment group, the number and percentage of subjects with a TEAE, serious TEAE, related TEAE, severe TEAE, TEAE leading to dose interruption, TEAE leading to study drug discontinuation, TEAE leading to study discontinuation, TEAE of special interest. This table will also include number of events. This display will be repeated for subgroups by randomization stratification variables.
- TEAEs by SOC and preferred term
- Serious TEAEs by SOC and preferred term
- Severe TEAEs by SOC and preferred term
- TEAEs by SOC, preferred term, and maximum severity
- Related TEAEs by SOC and preferred term
- TEAEs leading to study drug discontinuation by SOC and preferred term
- SAEs by stratification factors, SOC, and preferred term
- Most common TEAEs ($\geq 2\%$ or more of subjects in any treatment group) by preferred term
- AESIs by preferred term
- Related AESIs by preferred term
- AESIs by stratification factors and preferred term
- AESI incidence rate by SOC and preferred term
- Serious TEAE incidence rate by SOC and preferred term

- TEAEs leading to death incidence rate by SOC and preferred term
- Custom MedDRA query (CMQ) events (see Section [16.2](#)).

Unless specified otherwise, the following summary tables will be presented for the Discontinuation Period based on the Discontinuation Period Safety population:

- An overall summary showing for each treatment group, the number and percentage of subjects with a TEAE, serious TEAE, related TEAE, severe TEAE, TEAE leading to study discontinuation, treatment emergent AESI. This table will also include number of events. This display will be repeated for subgroups by randomization stratification variables.
- TEAEs by SOC and preferred term (for Double-blind Discontinuation Population and Double-blind Discontinuation Safety Population)
- Serious TEAEs by SOC and preferred term

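### SAP 9.2 sums risk time in days and calls it person-years; programmed literally, the rates for AESIs, serious TEAEs and TEAEs leading to death would be 365.25 times too small

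*SAP*

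**What the plan says.** SAP Section 9.2 introduces the rate and its scope in one sentence: "Incidence rate will be calculated for AESIs, serious TEAEs, and TEAEs leading to death, and will be summarized by SOC and preferred term". The rate is 1000 times the number of events over total person-years. Two definitions follow:

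- For the denominator, "total person-years is the sum across all subjects in the treatment group of the individual subject risk times".
- For each subject, "individual subject risk time is the number of days from first dose to the last day of the period" during which an event would be treated as treatment emergent.

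The list of double-blind tables in the same section then includes one incidence-rate table for each of the three outcomes.

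Section 9.2 contains no division by 365.25 and no other conversion from days to years. The protocol's adverse event analysis (Section 8.8.2) does not define this person-time rate, so SAP 9.2 is its only specification.

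Elsewhere the SAP writes the conversion out when it wants years. In Section 6.2, duration of pruritus is "Date of the Screening Visit – the start date of the pruritus+ 1)/365.25", and the other three baseline durations have the same form. When it wants days, as for treatment duration in Section 7, it labels the quantity as days.

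**The concern.** The definitions link together and leave no step at which days become years. A sum of day counts is person-days, but the SAP names it person-years. This differs from an omitted detail, because the denominator is fully specified and the specification is in the wrong unit.

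The rates concern serious events, deaths and the events singled out for special attention. SAP 9.2 plans no statistical tests on adverse events, so the rates are descriptive and their absolute size is what a reader would take from those tables.

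SAP Section 1 gives the SAP precedence over the protocol and requires deviations from it to be described in the study report. A programmer who sensibly divides by 365.25 is thus departing from the written definition, and one who follows it produces a wrong safety table.

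**Working it through.** The documents give no numerical incidence rate, so there is no stated figure to reproduce. The check compares the literal formula with the one that the label implies.

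**Inputs**

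- Multiplier 1000, and a denominator that is a plain sum of day counts: SAP 9.2.
- Days per year, 365.25: SAP 6.2.
- 175 subjects per arm: SAP 2.6.
- 85 days at risk per subject: an assumption. SAP Section 7 says that "the duration of double-blind treatment for each individual subject is expected to be 12 weeks", and a completer's end-of-treatment visit is on Day 85. Real windows will vary with early discontinuation and with the rule that ends the treatment-emergent window.
- 10 events: an assumption, for illustration only.

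**Formulas**, with E events and D total days at risk in an arm

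- Literal rate = 1000 × E / D
- Rate per 1000 person-years = 1000 × E / (D / 365.25)
- The second divided by the first = 365.25, whatever E and D are.

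**Numbers**

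- D = 175 × 85 = 14,875 days; 14,875 / 365.25 = 40.73 person-years.
- Literal: 1000 × 10 / 14,875 = 0.672.
- Converted: 1000 × 10 / 40.73 = 245.5 per 1000 person-years.

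**Range over the assumed inputs**

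| Subjects | Days each | Events | Person-years | Literal | Per 1000 person-years |
|---|---|---|---|---|---|
| 175 | 85 | 1 | 40.73 | 0.067 | 24.5 |
| 175 | 85 | 10 | 40.73 | 0.672 | 245.5 |
| 175 | 85 | 50 | 40.73 | 3.36 | 1227.7 |
| 175 | 60 | 10 | 28.75 | 0.952 | 347.9 |
| 250 | 85 | 10 | 58.18 | 0.471 | 171.9 |

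The rates move with the assumptions. The factor of 365.25 does not.

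**What cancels between arms and what does not.** Take 20 events in 175 × 85 = 14,875 days against 10 events in 175 × 83 = 14,525 days.

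- Literal rates: 1.345 and 0.688. Ratio 1.953, difference 0.656.
- Converted rates: 491.1 and 251.5. Ratio 1.953, difference 239.6.

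The ratio is unchanged. The difference is out by the same 365.25 as the rates.

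**The +1.** Section 9.2 does not say whether the first day is counted. From Day 1 to Day 85 is 84 days without the +1 and 85 with it. With 175 subjects and 10 events, the converted rate is 248.5 or 245.5, a difference of about 1%. This is a separate and much smaller matter than the unit.

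**The case against.** The strongest reply is that the sentence contradicts itself and so has no single literal result. The denominator is named person-years, and anyone who respects that name has to convert and will get the right rate. The fourfold use of 365.25 in Section 6.2 shows that the authors know the conversion. A literal result would also look odd: 0.672 per 1000 person-years beside ten events among 175 patients in about 12 weeks invites a second look.

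The consequences are limited too. The same formula applies to both arms, no planned test or decision rule uses the rate, and SAP 9.2 separately tabulates the same kinds of event by number and percentage of subjects.

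Much of this stands. The label makes years the likely intention, so the understatement depends on literal programming. It does not repair the definition: Section 6.2 covers baseline durations only, and the operative wording in 9.2 still counts days.

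A reader might infer two stronger things that the documents do not support:

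- **That the trial's reported rates are wrong.** The documents contain no computed rate, and a programmer may well have converted.
- **That double-blind and open-label rates would disagree 365-fold.** The protocol (Sections 8.1 and 8.5) does plan safety analyses across both phases, but SAP Sections 1 and 2.2.2 place the open-label analyses in a separate plan that is not among these documents. Its person-time definition is unknown.

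**Conclusion.** The definition in SAP 9.2 is wrong as written, for all three outcomes and not for AESIs alone. If it is programmed literally, the tables would show events per 1000 person-days under a person-years label, too small by exactly 365.25. That factor needs no assumption about events, numbers or follow-up. The illustrative pair of 0.672 and 245.5 rests on 175 subjects, 85 days each and 10 events.

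Absolute rates and between-arm rate differences would be wrong by that factor. Between-arm rate ratios, the hypothesis tests and the efficacy results are untouched, and so are the event counts and percentages. This is a specification error worth correcting because it governs serious-event and death rates and costs almost nothing to put right. It does not threaten the trial's conclusions.

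**What to change.** In SAP 9.2, define individual subject risk time in years as the number of days from first dose to the last day of the treatment-emergent window, divided by 365.25. State in the same clause that the day count includes the +1, so that risk time = (last day of window − date of first dose + 1) / 365.25. The division corrects the error. The +1 is a separate choice, made to match the exposure formula in SAP Section 7, with an effect of about 1% at 85 days.

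The cost is one clause. It needs no new data, no change to the design and no change to any other analysis.
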